2.3. Sample Size Calculation and Randomization

2.3.1. Sample Size Calculation

Sample size calculation is based on the primary endpoint, time to pericarditis recurrence defined as the time from randomization to the date of the first pericarditis recurrence for each subject. Time to pericarditis recurrence is assumed to follow an exponential distribution. An event of interest is defined as a subject's first adjudicated recurrence of pericarditis. The following assumptions are used in the sample size calculation using EAST 6.4.1:

- 1-sided significance level: 2.5%
- Power: 90%
- Median time to event (in weeks) in placebo: 8
- Hazard ratio (rilonacept/placebo): 0.244
- Percentage of subjects in the RI period that will not reach RW: 10%.

Given these assumptions, a total of 22 adjudicated pericarditis recurrence events is required to achieve the power. About 25 subjects per arm (a total of 50 subjects) or more will be randomized. Considering 10% of subjects in the RI period that will not reach the RW period, approximately 56 subjects will be enrolled in this study.

Subject enrollment and the pericarditis recurrence event accrual will be closely monitored during the study. The monitoring activities will be done in a blinded fashion during the RW period. If the number of subjects randomized is less than 50 and/or the time anticipated for the number of events required for the analysis of primary efficacy endpoint significantly exceeds the projected timeline, additional subjects may be enrolled and/or randomized at Kiniksa Pharmaceutical's discretion. However, at this time it is anticipated that no more than 100 subjects will be enrolled into this study.

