5.3.1. Adverse Events

Treatment-emergent AEs (TEAEs), defined as AEs that start or increase in severity after the first dose of study drug and before 6 weeks after the last dose of study drug, will be coded to system organ class and preferred term using MedDRA v21.1.

TEAEs will be summarized by each period and study overall. In the RW period, they will also be summarized by including and excluding bailout rilonecept, respectively. The average follow-up duration in weeks for TEAE will be provided in summary tables. The duration of follow-up for each subject is defined as follows.

- For the RI period, it is from first dose in RI period until the day before randomization, last dose day plus 6 weeks, last study day, or data cutoff, whichever occurs first.
- For the RW period including bailout, it is from randomization to data cutoff, last dose day plus 6 weeks, or last study day, whichever occurs first.
- For the RW period before bailout, it is from randomization to the start of using bailout rilonecept, data cutoff, last dose day plus 6 weeks, or last study day, whichever occurs first.
- For the LTE period, it is from first dose day in LTE period to data cutoff, last dose day plus 6 weeks, or last study day, whichever occurs first.
- For study overall, it is from first dose day in RI period to data cutoff, the last dose plus 6 weeks, or last study day, whichever occurs first.

A summary of the frequency (number and percentage of subjects) of TEAEs will be presented by system organ class and preferred term. Adverse events will also be analyzed by their severity (mild, moderate or severe), relationship to study drug, serious AEs, AEs leading to death, AEs resulting in dose interruption, AEs leading to withdrawal of study treatment, and AEs of injection site reaction.

Any AE of malignancy (excluding basal cell carcinoma of the skin) is of special interest. AE of special interest will also be summarized.

A subject experiencing the same AE multiple times will be counted only once for that preferred term. Similarly, if a subject experiences multiple AEs (preferred terms) within the same system organ class, then that subject will be counted only once for that system organ class. When summarizing by severity and relationship, only event with highest severity or relationship will be counted. All AEs will be presented by SOC and preferred terms.

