Incidence rate per 100 subject-years and its 95% CI will be calculated by the periods defined for follow-up duration above for the following groups of AEs:

- All AEs (include any AE),
- SAE (include any SAE),
- deaths,
- all infections (including serious),
- serious infections (serious only),
- all ISR (injection site reaction, including serious and non-serious),
- only serious ISR,
- all malignancies excluding NMSC (Non-Melanoma Skin Cancer: ie. cutaneous basal cell carcinoma and cutaneous squamous cell carcinoma).

Incidence rate per 100 subject-years = $100 \times (\text{number of different AE start days within the treatment period}) / (\text{Sum of treatment duration in years from all subjects in the cohort})$.

Multiple events within a subject will be counted as multiple events. Treatment exposure duration and follow-up of AE's in the Study Overall period will be 6 weeks after the last dose. There will be no formal hypothesis testing.

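### The RW before-bailout AE tables use crude percentages although follow-up is expected to be shorter on placebo, and the planned AE rates name a denominator that is not cut at bailout

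*SAP*

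**What the plan says.** All references are to SAP v2.0.

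- **Comparison.** Section 5.3 lists two RW safety comparisons of rilonacept with placebo, one including bailout rilonacept and one before it.
- **Follow-up.** Section 5.3.1: "For the RW period before bailout, it is from randomization to the start of using bailout" rilonacept, or to data cutoff, last dose plus 6 weeks or last study day if earlier. The rule is the same in both arms.
- **Measure.** Section 5.3.1: "A summary of the frequency (number and percentage of subjects) of TEAEs will be presented by system organ class and preferred term". AEs are also analyzed by severity and relationship, with each subject counted once. Average follow-up in weeks is printed in the tables.
- **Rates.** Section 5.3.1 plans incidence rates per 100 subject-years with 95% CIs, which "will be calculated by the periods defined for follow-up duration above for the following groups of AEs": all AEs, SAEs, deaths, all and serious infections, all and serious injection site reactions, and malignancies excluding non-melanoma skin cancer. The formula counts AE start days in the treatment period and divides by summed treatment duration.
- **Treatment duration.** The only RW definition is in section 5.1.6. It runs from first study drug to the earlier of last study drug plus 6 days and the end-of-RW visit, and does not mention bailout.
- **Laboratory rates.** Section 5.3.2 divides by follow-up duration.

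**The concern.** Bailout follows the efficacy event, so an effective drug lengthens its own before-bailout follow-up. The imbalance is therefore built into the design and does not arise by chance. Crude percentages of subjects with an event rise with time observed, so the arm observed longer is expected to show more events under equal hazards. Printing average follow-up reveals the imbalance but leaves the percentages as they are.

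This comparison matters because the alternative, including bailout, puts open-label rilonacept into the placebo arm. Safety is the stated secondary objective. A reader of the before-bailout tables could take an artefact of follow-up for a drug effect. The planned rates would be the natural safeguard, but if their denominator runs past bailout while their events stop there, they carry a bias in the same direction.

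**Working it through.** **Inputs (section 2.3.1).** "Time to pericarditis recurrence is assumed to follow an exponential distribution"; "Median time to event (in weeks) in placebo: 8"; "Hazard ratio (rilonacept/placebo): 0.244"; one-sided 2.5%; 90% power; about 25 subjects per arm.

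**1. Reproduce the plan's figure.** Schoenfeld: 4 × (1.960 + 1.282)² / (ln 0.244)² = 21.1, rounded up to 22. This agrees with "a total of 22 adjudicated pericarditis recurrence events is required to achieve the power".

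**2. Hazards.** Placebo: ln 2 / 8 = 0.0866 per week. Rilonacept: 0.244 × 0.0866 = 0.0211 per week.

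**3. Mean before-bailout follow-up.** If every recurrence leads to bailout at once (assumption), the mean over T weeks is m(T) = (1 − exp(−λT)) / λ. At T = 12, placebo is 7.5 weeks and rilonacept 10.6 weeks, a ratio of 0.70.

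**4. Tie T to the event-driven closure.** The SAP gives no RW length or accrual time. With 50 subjects planned at 1:1 and uniform accrual (assumption), closure is solved for 22 expected events. The last column uses an assumed 1 AE per subject-year (1/52 per week) in both arms.

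| Assumed accrual | Closure (week) | Randomized by then | Mean follow-up, placebo vs rilonacept (weeks) | Ratio | Crude AE %, placebo vs rilonacept |
|---|---|---|---|---|---|
| Simultaneous | 12.2 | 50 | 7.5 vs 10.8 | 0.70 | 13.2 vs 18.5 |
| 24 weeks | 25.7 | 50 | 7.3 vs 11.5 | 0.64 | 12.7 vs 19.1 |
| 36 weeks | 33.2 | 46 | 7.8 vs 13.3 | 0.58 | 13.2 vs 21.4 |
| 52 weeks | 42.5 | 41 | 8.5 vs 16.1 | 0.53 | 14.2 vs 24.9 |

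**5. Crude percentage over a fixed 12 weeks.** With AE hazard a in both arms, the expected percentage is a/(a+λ) × (1 − exp(−(a+λ)T)). At a = 0.02 per week (assumed):

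- placebo: 0.02/0.1066 × (1 − exp(−1.280)) = 13.5%
- rilonacept: 0.02/0.0411 × (1 − exp(−0.494)) = 18.9%

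The ratio is 1.40 with no drug effect. At a = 0.005 per week, nearer to a single uncommon term, it is 3.6% vs 5.2%, or 0.9 vs 1.3 subjects of 25.

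**6. Recurrences without bailout.** If only a share f leads to bailout (assumed), mean follow-up is f·m(T) + (1 − f)·T. At 12 weeks the ratio rises from 0.70 to 0.79 (f = 0.75) or 0.86 (f = 0.50).

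**7. The planned rates.** Over before-bailout follow-up, the expected rate is a in both arms, so the rate ratio is 1. If before-bailout events are divided by a duration that runs to T, the rate shrinks by m(T)/T. At 12 weeks this is 0.62 on placebo and 0.88 on rilonacept, an apparent ratio of 0.88/0.62 = 1.42. At 24 weeks it is 0.42 and 0.78, a ratio of about 1.86.

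**The case against.** The strongest reply is that the SAP already deals with most of this. Average follow-up is in the tables, the broad AE groups have rates by the same periods, safety is descriptive without formal testing, and rates for sparse terms are imprecise. What stands is that SAEs, infections, injection site reactions and malignancies should not be listed as lacking a rate. The gap is in the system organ class/preferred term, severity and relationship tables.

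Three stronger readings are tempting, and the documents do not support them.

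- **That placebo is observed for about half as long.** The SAP states no RW length. A common follow-up of 24 weeks gives a ratio of 0.54, but by then 31.8 events would be expected among 50 subjects, well past closure at 22. Among the accrual patterns in the table, only 52-week accrual comes near half, and then only 41 subjects are randomized at closure against a plan of 50 or more. Section 2.1 also keeps subjects who recur without meeting the bailout criteria on blinded drug, which narrows the gap.
- **That every term will show an excess on rilonacept.** This is true only in expectation. For uncommon terms the shift is a fraction of a subject and lies within chance.
- **That the placebo group is free of rilonacept.** All randomized subjects received it in the run-in.

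On the denominator, the sentence introducing the rates points to the follow-up periods, and last study drug could be read as the last blinded dose, which would end the duration near bailout. The text is therefore open to two readings. But the formula names treatment duration, and the section 5.1.6 definition contains no bailout cut.

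The later SAP addendum (section 3.2) limits safety summaries to the run-in, RW and long-term extension periods. It does not say that the bailout split within RW is dropped.

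**Conclusion.** The point holds in direction, with a moderate and assumption-dependent size. Under the SAP's exponential sizing figures, with 50 subjects planned and closure at 22 expected events, mean before-bailout follow-up on placebo is about 0.53 to 0.70 of that on rilonacept. This rests on accrual between simultaneous entry and 52 weeks and on bailout after every recurrence; the ratio moves toward 1 otherwise. Crude percentages in the term, severity and relationship tables are then expected to be higher on rilonacept with no drug effect. The planned rates do not reliably correct this, because their stated denominator, taken literally, runs past bailout. The primary efficacy analysis is not affected. This should be corrected, at the level of safety presentation.

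**What to change.** 1. **Section 5.3.1, RW before-bailout tables** (system organ class/preferred term, severity, relationship): next to n (%), add subjects with a first event per 100 subject-years. Use the before-bailout follow-up already defined there, stopped at the first event. State that the between-arm reading rests on the rate.
2. **Section 5.3.1, rate formula:** replace treatment duration and treatment period with the period-specific follow-up duration defined in the same section, as section 5.3.2 does for laboratory rates.

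The cost is SAP wording and one extra column; the follow-up variable is already defined and the exact rate CI is in section 13.4. Rates for rare terms will be imprecise. The rate corrects for time at risk only: if stopping at bailout is related to AE risk, that bias remains.

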5.1.6. Study Drug Administration

The study medication administration details including the administration date and time, dose, site of injection and comments will be presented in a by-subject listing.

The following parameters related to study drug administration will be summarized for each of the treatment periods: RI, RW, LTE, and Study Overall.

- Treatment duration in weeks:
 - For RI period, it is defined as [minimum of (date of last study drug +6, date of RI week 12 visit – 1, date of data cutoff) - date of first study drug + 1)/7].
 - For RW period it is defined as [minimum of (date of last study drug +6, date of end of RW visit) - date of first study drug + 1)/7].
 - For LTE and study overall, it is defined as [minimum of (date of last study drug +6, end of study date, date of data cutoff) - date of first study drug + 1)/7].

Number of administrations in each period regardless of full amount or partial amount of syringe injected. The loading dose includes two injections and will be counted as one administration.

Compliance (%) in each period, calculated as (number of administrations) / (protocol planned number of administrations) × 100%. The loading dose includes 2 injections and will be counted as one administration.

Total riloncept dose administered in each period, defined as the sum of all doses (mg) received in the corresponding period. The actual volume administered will be used to calculate the total dose. For subjects receiving weight-adjusted dose (e.g., 2.2 mg/kg) their weight collected at scheduled visits will be used to calculate the amount of the study drug received.

Percentage of self-administrations by the subject, defined as [Number of self-administrations] / [Total number of administrations received] × 100%. The loading dose will be included in the denominator as one administration. If one of 2 injections in the loading dose is self-administered, it will be counted in the numerator.

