5.3.2. Clinical Laboratory Parameters

Hematology, chemistry, lipid panel, and urinalysis results will be summarized and listed. Pregnancy test will not be summarized but will be listed. Summaries will include descriptive statistics for actual values and change from baseline. Shift tables from baseline condition to the condition at each visit will also be provided. The shift table will include subjects without data so that all subjects in the safety population at the baseline of each period (RI, RW, and LTE) will be included.

A summary of hepatic function abnormalities will be provided for the following criteria:

- >2xULN
- >3xULN
- >5xULN
- The number of percentage of subject's meeting the criteria for Hy's Law defined as elevations in ALT and/or AST of $\geq 3xULN$ with accompanying elevations in total bilirubin of $\geq 2xULN$ will also be summarized.

The incidence rate per 100 subject-years and its 95% CI for the following lab abnormalities will be calculated:

- Incidence of ALT >5xULN,

- Incidence of AST >5x ULN,
- Incidence of total bilirubin >2xULN
- Incidence of absolute neutrophil count (ANC) <1.0 x 10³ uL.

Multiple lab abnormalities within a subject will be counted as multiple events within the follow-up period defined in Section 5.3.1 .

Incidence rate per 100 subject years in a cohort = $100 \times (\# \text{ of different lab abnormalities from all subjects within the follow-up period}) / (\text{Sum of follow-up duration in years from all subjects in the cohort})$.

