13.4. Calculation of 95% CI for Incidence Rate per 100 Subject-Years of Exposure/Observation

We first construct a formula to calculate the exact $100(1-\alpha)\%$ 2-sided CI for the number of events in a time interval. When this formula is applied to the number of events in a time interval of 100 subject-years in a study, we obtain the desired result to construct Fisher's exact 2-sided $100(1-\alpha)\%$ confidence interval for an incidence rate of interest per 100 subject-years. When $\alpha = 0.05$, it provides a 95% CI.

The number of events of interest in a time interval can be modelled using a Poisson distribution with parameter λ , where λ is the average number of events in this time interval. The probability of observing k events in this time interval is:

$$P(k \text{ events in interval}) = e^{-\lambda} \frac{\lambda^k}{k!}$$

If k events were observed in the interval, the lower bound l and upper bound u of the $100(1-\alpha)\%$ CI must satisfy the following conditions for Fisher's exact CI:

$$\text{Lower bound: } \sum_{x=0}^k \frac{e^{-l} l^x}{x!} = 1 - \alpha / 2$$

$$\text{Upper bound: } \sum_{x=0}^k \frac{e^{-u} u^x}{x!} = 1 - \alpha / 2$$

The parameter λ can be estimated with k . Using the relationship between the cumulative distribution functions of the Poisson and chi-squared distributions, the above lower and upper bounds can be expressed as follows:

$$\frac{1}{2} x^2 \left(\frac{\alpha}{2}; 2k \right) \leq \lambda \leq \frac{1}{2} x^2 \left(1 - \frac{\alpha}{2}; 2k + 2 \right), \quad (1)$$

where $x^2(a; v)$ is the chi-square quantile for lower tail probability with v degrees of freedom.

The inequalities in (1) are used in the SAS macro below to construct the confidence interval for the number of events. The lower bound, number of events, and upper bound are divided by the total treatment exposure expressed as subject-year to construct the incidence rate and its CI. Each number is then multiplied by 100 to obtain the incidence rate per 100 subject-years.

SAS Macro for the 95% CI of incidence rate per 100 subject-years

```

%macro nppy(x=5, n=100, alpha=0.05);
***   x=5 --# of events;
***   n = # of subject-years.;
***   alpha=2-sided type-I error rate, alpha=0.05 for 95% CI.;

data temp;
x=&x;
n=&n;
alpha=α
length CI_coverage $12.;
CI_coverage=compress(round(100*(1-&alpha), 0.1))||'%';
r=round((x/n)*100, 0.001);
if x=0 then Lower_bound=0;
else Lower_bound = round((quantile('CHISQ',&alpha/2,2*&x)/2/n)*100, 0.001);

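### AE incidence rates are to be given by follow-up period but are divided by treatment duration, which has no pre-bailout version for the randomized withdrawal (RW) period

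*SAP*

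**What the plan says.** All references are to SAP v2.0 unless stated.

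- **Section 5.3.1, follow-up.** Five follow-up periods are defined. Two concern RW. Including bailout, time runs from randomization to cutoff, last dose plus 6 weeks or last study day. The other is shorter: "For the RW period before bailout, it is from randomization to the start of using bailout" rilonacept, or to one of those same limits if earlier.
- **Section 5.3.1, rates.** "Incidence rate per 100 subject-years and its 95% CI will be calculated by the periods defined for follow-up duration above". The formula's numerator is the "number of different AE start days within the treatment period" and its denominator the "Sum of treatment duration in years from all subjects in the cohort". The text then adds: "Multiple events within a subject will be counted as multiple events". No hypothesis is tested. For Study Overall only, exposure and follow-up are both set to end 6 weeks after the last dose.
- **Section 5.1.6, treatment duration.** "For RW period it is defined as [minimum of (date of last study drug +6, date of end of RW visit"), less the first dose date, plus one day. There is no other RW version. Study Overall here ends at last dose + 6 days.
- **Section 5.3.2, laboratory rates.** The denominator is the "Sum of follow-up duration in years from all subjects in the cohort".
- **Section 13.4.** Counts and confidence limits are divided by total treatment exposure. "The number of events of interest in a time interval can be modelled using a Poisson distribution", and exact limits follow from that.
- **LTE addendum, Section 3.2.** Safety summaries are limited to RI, RW and LTE.

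**The concern.** Section 5.3 requires RW safety summaries both including and before bailout. The before-bailout contrast is the only randomized safety comparison not mixed with open-label rilonacept. Two rates over different observation windows need two denominators, and treatment duration supplies only one for RW. Placebo subjects are expected to reach bailout sooner, so a denominator that runs on past bailout would shrink the placebo rate more than the rilonacept rate.

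Three smaller problems share the same formula:

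- AEs can be counted to last dose + 6 weeks over time that ends at last dose + 6 days.
- Counting distinct start days merges two AEs that begin on one day, while the next sentence counts every event.
- All repeat AEs in a subject enter a Poisson interval that makes no allowance for differences between subjects.

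**Working it through.** **1. What each reading gives for RW**

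| Reading | Before-bailout rate | Including-bailout rate |
|---|---|---|
| Follow-up wording governs numerator and denominator | consistent | consistent |
| Literal formula, same RW treatment span in numerator and denominator, bailout counted as study drug | equals the including-bailout rate, so mislabelled | consistent, apart from the window after last dose |
| Numerator cut at bailout by 5.3.1, denominator from 5.1.6, bailout counted as study drug | diluted | consistent, apart from the window after last dose |
| Denominator from 5.1.6, bailout not counted as study drug | roughly consistent | AEs during bailout over time that excludes it, so inflated |

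Only the first reading leaves both rates sound, and it requires treatment duration to mean something other than its Section 5.1.6 definition.

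**2. The plan's own figure (Section 2.3.1)**

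Inputs: one-sided 2.5%, 90% power, HR 0.244, 1:1 allocation. Schoenfeld events = 4(1.960 + 1.282)² / (ln 0.244)² = 42.03 / 1.990 = 21.1, so 22 as stated. Power at 22 events is 91.1%.

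**3. Size of the dilution under the third reading**

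Inputs from Section 2.3.1: exponential times, placebo median 8 weeks, 25 subjects per arm. Assumed: every recurrence is bailed out at once.

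- Placebo λ = ln 2 / 8 = 0.0866 per week; rilonacept 0.244 × 0.0866 = 0.0211.
- Mean pre-bailout time over an RW length T is (1 − e^(−λT)) / λ. Dividing by T gives the diluted rate relative to the follow-up-based rate.
- Example, T = 12: placebo (1 − 0.3536) / 0.0866 = 7.46 weeks, and 7.46 / 12 = 0.62. Rilonacept: 10.60 / 12 = 0.88. Expected events 21.8, close to 22.

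| T (weeks) | Placebo | Rilonacept |
|---|---|---|
| 8 | 0.72 | 0.92 |
| 12 | 0.62 | 0.88 |
| 16 | 0.54 | 0.85 |
| 20 | 0.48 | 0.82 |
| 24 | 0.42 | 0.78 |
| 36 | 0.31 | 0.70 |

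With uniform entry over an assumed 12, 26, 40 or 52 weeks and closure when 22 events are expected, the placebo factor is 0.60, 0.53, 0.45 or 0.40. In the last two cases closure comes with only about 45 and 41 of the 50 planned subjects entered. A separate simulation gave full-to-pre-bailout person-time ratios at 26 and 52 weeks of 1.86 and 2.42 on placebo (factors 1/1.86 = 0.54 and 1/2.42 = 0.41) and 1.19 and 1.30 on rilonacept (0.84 and 0.77).

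If only 75% of recurrences lead to bailout, the placebo factor is (0.75 × pre-bailout mean + 0.25 × T) / T: 0.72, 0.66 and 0.57 at T = 12, 16 and 24.

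**4. The window after last dose**

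42 − 6 = 36 days at most per subject who stops dosing and is followed. For a subject stopping at week 12, (84 + 42) / (84 + 6) = 1.40, so person-time is understated 1.40-fold and the rate can be overstated. Against 24 months of LTE (about 730 days), 36 / 730 is about 5%. Randomized subjects have no gap at the end of RI, because both definitions stop the day before the Week 12/randomization visit.

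**5. The Poisson interval**

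Neither AE frequency nor dispersion is in the SAP, so both are assumed. With mean μ events per subject and gamma between-subject variance k, the count variance is inflated by 1 + kμ. At μ = 2 and k = 1 this is 3, and the interval should be √3 = 1.73 times wider.

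- Simulated coverage of nominal 95% limits at μ = 2, 30 subjects: 96%, 86%, 77% and 64% at k = 0, 0.5, 1 and 2.
- With 25 subjects followed 0.5 year at 4 events per subject-year (also μ = 2), coverage at k = 1 was 75%.
- At μ = 1, 30 subjects: 96%, 90%, 85% and 76%.

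**The case against.** The best defence is that the lead-in ties the rates to the follow-up periods, so treatment duration is loose wording and nothing is diluted. That reading is available, but the text does not settle on it. Treatment duration is a defined term, Section 13.4 repeats the exposure denominator, and the one sentence that equates exposure with follow-up covers Study Overall only, a period the LTE addendum then leaves out.

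A reader might infer that the plan halves the pre-bailout placebo rate. The documents do not establish that:

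- It needs a numerator taken from 5.3.1 and a denominator from 5.1.6.
- It needs bailout to count as study drug, and usage varies. Section 2.1 times bailout from the last study drug injection, and note u of Table 5 lists blinded study drug and open-label rilonacept separately, whereas Section 4.4 calls LTE dosing study drug.
- It needs prompt bailout of every recurrence, although Section 2.1 keeps subjects who do not meet the bailout criteria on blinded drug.
- It needs an accrual time that the SAP does not give.

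A reader might also infer that the denominator is treatment time over the whole study. It is not: Section 5.1.6 is period-specific, and only the pre-bailout version is missing.

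Nor can one say outright that the intervals are too narrow. With no between-subject variation the exact Poisson limits hold their 95%.

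It is also true that no rate ratio is planned, and that pre-bailout counts and percentages with average follow-up are reported alongside. Distinct start days could be the working rule for counting repeat events, but the SAP does not say so, and the two statements give different counts when two AEs start on the same day.

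**Conclusion.** The point stands as an unresolved conflict between the rate's stated periods and its denominator. Unless the follow-up wording is made to override the formula, at least one RW rate is mismatched or mislabelled.

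The direction of error is not fixed. Under the assumptions in step 3, the pre-bailout placebo rate falls to about 0.4 to 0.6 of its follow-up-based value on the planning inputs, and to 0.31 to 0.72 across RW lengths of 8 to 36 weeks, with a much smaller fall on rilonacept. The window after last dose works the other way, raising rates, and only for subjects who stop dosing and are followed.

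The interval point is secondary and conditional on AE counts varying between subjects. It is relevant to all AEs, all infections and all injection site reactions (ISR), not to deaths, and it matters little for malignancies. Because the rates are descriptive, severity is modest, but the correction is cheap and worth making.

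**What to change.** - Replace the formula in Section 5.3.1 with: rate = 100 × (AEs with onset in the 5.3.1 follow-up period) / (sum of that same period's 5.3.1 follow-up in years), including the before-bailout version. Remove treatment duration from it.
- Align Section 13.4, so that counts and limits are divided by the same follow-up time.
- State one event-count rule in place of the two now given.
- For all AEs, all infections and all ISR, add a subject-clustered interval, such as robust-variance Poisson or a subject bootstrap. Keep the exact Poisson limits for deaths and for sparse or zero-event categories, where a bootstrap collapses to zero width and a robust interval fails.

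The cost is SAP wording and a small programming change. The downside is wider intervals for frequent AEs.

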5.1.5. Prior and Concomitant Medications

Prior medications are defined as those taken before the date of the first study drug administration, i.e. started before the start of the study drug.

Concomitant medications are defined as any non-study medication taken during the treatment period which is from the date of first dose to the date of last dose plus 6 weeks.

Additionally, the medications will be considered concomitant if the start date of the medication is missing.

A medication that started prior to the first dose of the study drug and continued after that date will be considered as both prior and concomitant.

Prior and concomitant medications will be coded using World Health Organization (WHO) Drug (version March 2018). Medications will be summarized by ATC level 2 code and preferred term. Summary will be done by periods (i.e., RI, RW, and LTE) and by treatment (KPL-914 vs placebo) for RW period. One subject will be counted once within one preferred term and one ATC class. The medication information will be presented in a by-subject listing with ATC class (level 2) and WHO Drug Dictionary preferred term, start and stop date, dosage, route, frequency and indication.

Concomitant pericarditis treatment will be summarized by period and by treatment for RW period using the following categories:

- Analgesics
 - Non-opioid analgesics
 - Opioid analgesics
- Nonsteroidal anti-inflammatory drug (NSAIDs)
 - Aspirin
 - Other NSAIDs
- Colchicine
- Corticosteroids
 - Oral corticosteroids
 - IM/IV corticosteroids
- Other

In addition, concomitant pericarditis treatment received during the RW treatment period will also be summarized based on the status of receiving bailout treatment (i.e. concomitant

medication received before start of bailout treatment vs after start bailout treatment) for each treatment group in the RW period.

For RI period, use of concomitant pericarditis treatment (i.e., background treatment) will be summarized over time.

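### AE incidence rates: events are counted over follow-up windows but divided by treatment duration, which ends 36 days earlier and has only one value for the RW period

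*SAP*

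**What the plan says.** All references are to SAP v2.0 unless stated.

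- **Windows (5.3.1).** Follow-up for TEAEs is defined for RI, RW including bailout, RW before bailout, LTE and study overall. Each window can run to six weeks after the last dose. For the before-bailout display, "it is from randomization to the start of using bailout" rilonacept or an earlier stopping point. Incidence rates "will be calculated by the periods defined for follow-up duration above for the following groups of AEs".
- **Numerator (5.3.1).** The formula counts the "number of different AE start days within the treatment period". The SAP describes a treatment period in 5.1.5, for concomitant medications: "during the treatment period which is from the date of first dose to the date of last dose plus 6 weeks".
- **Denominator (5.3.1).** "Sum of treatment duration in years from all subjects in the cohort". Appendix 13.4 likewise divides by treatment exposure in subject-years.
- **Treatment duration (5.1.6).** RI ends at the "minimum of (date of last study drug +6, date of RI week 12 visit – 1, date of data cutoff"). For RW there is one definition: "For RW period it is defined as [minimum of (date of last study drug +6, date of end of RW visit"). LTE and study overall also stop six days after the last study drug at the latest. Nothing is split at bailout, and the text does not say whether study drug in RW includes open-label bailout.
- **Laboratory rates (5.3.2).** These count abnormalities within the follow-up period and divide by the "Sum of follow-up duration in years from all subjects in the cohort".
- **Exception.** One sentence after the AE formula sets exposure and AE follow-up both to six weeks after the last dose, but only for study overall. Section 3.2 of the later addendum restricts safety summaries to RI, RW and LTE.

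**The concern.** A rate per subject-year is interpretable only if every day on which an event can be counted is also a day of person-time. Here the counting windows and the denominator are defined in different sections and end at different points. The outputs include serious AEs, deaths and serious infections with exact confidence intervals, shown by arm in RW. In RW, time to bailout depends on recurrence, which the treatment is meant to delay. An error in handling bailout time would therefore not cancel between arms.

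**Working it through.** The SAP states no AE rate and no subject-year total, so there is no figure to reproduce. The check compares the two definitions and then sizes the gap.

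**1. Subjects who stop drug before the period ends**

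The AE window ends at last dose + 42 days and treatment duration at last dose + 6 days, so the gap is 42 − 6 = 36 days (36/365.25 = 0.099 subject-years).

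For n weekly doses with no other truncation:
- treatment duration = 7(n − 1) + 6 + 1 days
- follow-up = 7(n − 1) + 42 + 1 days

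| Doses | Treatment duration (days) | Follow-up (days) | Ratio |
|---|---|---|---|
| 5 (RI, last dose at Week 4) | 28 + 7 = 35 | 28 + 43 = 71 | 2.03 |
| 12 | 84 | 120 | 1.43 |
| 24 | 168 | 204 | 1.21 |
| 52 | 364 | 400 | 1.10 |

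The ratio is the factor by which that subject's contribution to the rate is overstated if AEs occur evenly over time. It applies only to subjects who stop. In RI the two definitions coincide for anyone randomized at Week 12, since both end the day before that visit. In RW and LTE they largely coincide for subjects dosed up to the end of the period.

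**2. One RW denominator for two RW displays**

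- *If study drug includes bailout:* the single RW duration carries post-bailout time. The before-bailout rates are then diluted, more in placebo.
- *If study drug means blinded drug only:* the duration ends near the start of bailout. The including-bailout rates then lack post-bailout time, again mostly in placebo, and are inflated there.

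To size the first reading, take the sizing inputs in 2.3.1: exponential times, placebo median 8 weeks, hazard ratio 0.244. Assume bailout at every recurrence, no other stopping, and a fixed RW length of T weeks.

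- Placebo hazard: λ₀ = ln 2 / 8 = 0.0866 per week
- Rilonacept hazard: λ₁ = 0.244 × λ₀ = 0.0211 per week
- Mean pre-bailout time: m = (1 − exp(−λT)) / λ
- Dilution factor in each arm: T / m
- Apparent rilonacept/placebo ratio when true rates are equal: m₁ / m₀

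| T (weeks) | m₀ placebo | m₁ rilonacept | T/m₀ | T/m₁ | Apparent ratio |
|---|---|---|---|---|---|
| 16 | 8.66 | 13.57 | 1.85 | 1.18 | 1.57 |
| 24 | 10.10 | 18.82 | 2.38 | 1.28 | 1.86 |
| 36 | 11.03 | 25.20 | 3.26 | 1.43 | 2.28 |

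Under the second reading the before-bailout display is nearly right and the error moves to the including-bailout display. At T = 24, taking the blinded-drug duration as close to the pre-bailout time, the apparent ratio there would be 10.10 / 18.82 = 0.54. That is the opposite direction.

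**The case against.** **The terms can be read so that they match.** If treatment duration means the length of the 5.1.5 treatment period, or if treatment period means on-drug time, numerator and denominator agree. Each route has to set something aside. The first ignores 5.1.6, the only place where treatment duration is defined. The second ignores the lead-in to the formula, which ties the rates to the follow-up windows. The explicit six-week exception for study overall also suggests that the other periods are meant to follow 5.1.6.

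**The lead-in already directs the analyst to the right windows.** That may well be the intent, and it makes the full-RW denominator a literal reading rather than a certain one. The formula still names a different quantity, and 5.3.2 shows that the plan words it differently when it means follow-up.

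**The reach of the 36-day gap is limited.** This stands. The sizing assumes that 10% of RI subjects do not reach RW, and subjects dosed to period end are hardly touched.

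**The RW figures lean on strong assumptions.** This also stands. Bailout requires both pain NRS ≥ 4 and CRP ≥ 1 mg/dL, whereas the second and third CEC criteria confirm recurrences below one of those thresholds. RW is event-driven, so its length is unknown and not common to all subjects.

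**A tempting stronger inference** is that the plan makes rilonacept look more harmful than placebo. The document does not support it. That direction holds only if RW treatment duration includes bailout time. If it stops at blinded drug, the affected display changes and the error runs the other way.

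**Conclusion.** The inconsistency is real and should be corrected. As written, the AE rate formula can pair events from one window with person-time from another. For subjects who stop drug before the period ends, the shortfall is up to 36 days each. In RW, no single denominator is right for both displays, and the error falls mainly on the placebo arm; its direction is undetermined. The ratios 1.57, 1.86 and 2.28 describe one conditional scenario on the bailout-included reading and are not a prediction.

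The consequence is confined to descriptive safety rates and their confidence intervals. Section 5.3.1 rules out formal testing, and the TEAE tables also give subject counts, percentages and average follow-up.

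**What to change.** In the 5.3.1 rate formula, replace treatment period and treatment duration with the follow-up period and follow-up duration already defined for the display concerned: RI, RW before bailout, RW including bailout, or LTE. This is the form 5.3.2 uses for laboratory abnormalities. In 13.4, change the divisor from treatment exposure to the same follow-up duration.

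The cost is one sentence in 5.3.1 and a matching phrase in 13.4. No new derivation is needed, because these durations are already required for the average follow-up shown in the TEAE tables.
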